4.2.3 General Imputation Rule for Incomplete Dates

Where necessary for the calculation of derived variables (e.g., age), partial dates will be imputed using the earliest calendar date based on the partial date provided. This rule is valid for all partial dates with the exception of the following:

- Start and stop dates of AEs
- Start and stop dates of prior and concomitant medication
- Stop dates of past and concomitant diseases
- Patch application dates

Completely missing dates will not be replaced, and the corresponding derived variables will be set to missing.

5 STUDY POPULATION CHARACTERISTICS

Study population characteristics will be summarized for the SS and by final dose group and all subjects combined.

5.1 Subject disposition

Subject disposition will be presented in terms of the number of subjects who

- completed or withdrew (including reasons) during the study
- started the Titration Period (attended Visit 2 and was treated) and subsequently completed (attended Visit 5) or withdrew (including reasons) during the Titration Period
- started the Maintenance Period (attended Visit 5) and either completed or withdrew (including reasons) during the Maintenance Period
- started and completed the Taper Period, with reasons if applicable
- and completed the Safety Follow-up Period or withdrew (including reasons) prior to the Safety Follow-up visit

Subjects will be counted as completed study and maintenance period, if they don't withdraw before EoM, and as completed titration, taper, and safety follow-up periods, if they don't withdraw before the end of the respective period.

Summaries will also be provided for discontinuations due to AEs and disposition of analysis sets. Reasons for screen failure will be listed.

5.2 Protocol deviations

All important protocol deviations will be listed.

6 DEMOGRAPHICS AND OTHER BASELINE CHARACTERISTICS

6.1 Demographics

Age will be derived in years applying all rules for missing date imputation as described in [Section 4.2.3](#) as integer ((Date of informed consent - date of birth) / 365.25).

Weight recorded in pounds (lb) will be converted to kilograms (kg) as weight(lb)*0.4536kg/lb.

Height recorded in inches (in) will be converted to height in centimeters (cm) as height(in)*2.54cm/in.

The BMI will be calculated as weight (kg) / (height (m))².

The following demographics will be summarized:

- Age (years)
- Age (EudraCT age categories)
- Age (clinicaltrials.gov age categories)
- Gender (Male; Female)
- Racial Group (American Indian/Alaskan Native; Asian; Black; Native Hawaiian or Other Pacific Islander; White; Other/Mixed)
- Ethnicity (Hispanic or Latino; Not Hispanic or Latino)
- Weight (kg)
- Height (cm)
- BMI (kg/m²)
- BMI (<18.5, 18.5-<25, 25-<30, 30-<35, 35-<40, >=40, Missing)

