UCB has completed a Phase 2 pharmacokinetic (PK)/pharmacodynamic (PD) study in adolescent subjects 13 to 17 years of age, which showed a PK profile similar to that in adult subjects. Although the study was open-label and the sample size was small, the efficacy of rotigotine transdermal system in adolescent subjects also appeared similar to efficacy in adults. Improvements were observed in most efficacy parameters, including the IRLS, CGI Items 1 through 3, and RLS-6, indicating improvements in RLS symptoms and sleep. The purpose of this study is to further investigate the safety, tolerability, and efficacy of rotigotine in adolescent subjects 13 to 17 years of age.

A remote study model will be used to conduct this study. This model integrates telemedicine technology into the clinical research process and supports management of research activities, including data collection. As part of this model, study visits are completed using the unique technology platform called Science 37 Platform (PLATFORM), which is the backbone of the studies conducted via this model. PLATFORM is the software interface that connects subjects/legal representatives to their investigators/study teams through a study-issued smartphone. This technology will be used in combination with visits from mobile study personnel to subjects'/legal representatives' homes.

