6 SELECTION AND WITHDRAWAL OF SUBJECTS

6.1 Inclusion criteria

To be eligible to participate in this study, all of the following criteria must be met:

1. An Institutional Review Board (IRB)-approved written Informed Consent form is signed and dated by the subject or by the parent(s) or legal representative. The Informed Consent form or a specific Assent form, where required, will be signed and dated by minors.
2. Subject/legal representative is considered reliable and capable of adhering to the protocol (eg, able to understand and complete all questionnaires and diaries), visit schedule, or medication intake according to the judgment of the investigator.
3. Subject weighs $\geq 40\text{kg}$.
4. Subject has completed at least one dose step in SP1006, a previous study of rotigotine in adolescents with RLS, without meeting withdrawal criteria.
5. Female subjects must be surgically incapable of childbearing, or effectively practicing an acceptable method of contraception (oral/parenteral/implantable hormonal contraceptives, intrauterine device, or barrier and spermicide). Abstinence is an acceptable method. Subjects must agree to use adequate contraception during the study and for 4 weeks after their final dose of study drug.
6. Subject is expected to benefit from participation, in the opinion of the investigator.

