2.1.2.2 Other safety variables

Other safety variables are:

- Changes from Baseline in 12-lead electrocardiograms (ECGs)
- Changes from Baseline in vital signs (including orthostatic assessment)
- Changes from Baseline in hormone status
- Changes from Baseline in laboratory data (hematology, blood chemistry, and urinalysis)
- Changes in menstrual function for all female subjects
- Changes from Baseline in Modified Minnesota Impulsive Disorder Interview (mMIDI)
- Changes from Baseline in body weight, height, and calculated body mass index (BMI)

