10.4 Vital signs, physical findings, and other observations related to safety

10.4.1 Vital signs

Summary statistics of the observed values and changes from Baseline for vital sign parameters (systolic and diastolic blood pressure, and pulse rate) will be presented by visit and final dose group for supine measurements (after 1 and 5 minutes) as well as standing measurements (after 1 and 3 minutes). Observed values and change from Baseline values will also be presented for the orthostatic reaction after 1 and 3 minutes standing.

Orthostatic hypotension will be assessed using the difference between supine and standing systolic and diastolic blood pressure at each visit. For systolic BP, diastolic BP and pulse, the difference will be calculated using the 5-minute supine values with both the 1 and 3 minute standing values for each parameter, respectively. A drop in systolic BP of ≥ 20 mmHg or a drop in diastolic BP of ≥ 10 mmHg after 1 or 3 minutes in the standing position is indicative of orthostatic hypotension.

A listing of results for vital signs, and body weight, BMI, temperature, respiratory rate, height and height percentile (based on CDC growth charts at <http://www.cdc.gov/growthcharts>) will be provided. A separate listing for orthostatic hypotension will also be provided.

10.4.2 *Electrocardiograms*

Summary statistics of the observed values and changes from Baseline for ECG parameters (Heart rate, RR interval, PQ/PR interval, QRS duration, QT interval, QTcB interval, and QTcF interval) will be presented by visit.

ECG results and findings will be listed.

10.4.3 *Modified Minnesota Impulsive Disorders Interview*

Assessments of mMIDI will only be listed.

10.4.4 *Physical and neurological examinations*

Physical and neurological examination abnormalities will be listed only. Changes in menstrual function will also be listed.

10.4.5 *Suicide ideation and behavior*

[figure not shown]
Suicide ideation and behavior will be measured using the Columbia-Suicide Severity Rating Scale (C-SSRS). Results of the C-SSRS will only be listed.

11 *OTHER ANALYSES*

11.1 *Subject Quality of Life Questionnaire.*

The restless legs syndrome quality of life (RLS-QoL) (Kohnen, 2002) will be used to evaluate quality of life. This disease-specific instrument consists of 12 questions with numeric outcome (0 – 5). The RLS-QoL total score will be calculated as the sum of all 12 items.

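### The SAP reads height against the CDC growth charts but not weight or BMI, and groups adolescents' BMI in fixed bands that ignore age and sex

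*SAP*

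**What the plan says.** - **Population.** Protocol section 2 places the trial in "adolescent subjects 13 to 17 years of age". Inclusion criterion 3 (protocol 6.1) sets a minimum weight of 40 kg.
- **Demographic table.** SAP 6.1 summarises age, weight, height and BMI, and also groups BMI: "BMI (<18.5, 18.5-<25, 25-<30, 30-<35, 35-<40, >=40, Missing". The bands have no labels and do not vary by age or sex.
- **Safety variable.** SAP 2.1.2.2 declares "Changes from Baseline in body weight, height, and calculated body mass index (BMI"). Protocol 4.1.2 declares the same variable, with Baseline taken from SP1006.
- **Display after baseline.** SAP 10.4.1 plans "A listing of results for vital signs, and body weight, BMI, temperature, respiratory rate, height and height percentile (based on CDC growth charts at" the CDC site). The growth reference is attached to height alone. No table of weight, height or BMI by visit is planned. SAP 3.1 has the listings carry derived values such as change from Baseline.
- **Protocol intention.** Protocol 13.4.2 planned summary statistics for body weight, height and BMI.
- **Early termination.** SAP sections 1 and 3.9 and the SAP amendment log say that displays were cut because the study stopped early. They do not name body size.

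**The concern.** Adolescents are expected to gain height and weight during a study of this length, and there is no control arm to show how much. A listed weight change then mixes ordinary growth with any effect of treatment. A gain may be growth alone. An unchanged weight may be a shortfall.

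The usual remedy is to express each measurement relative to a reference for age and sex. The SAP accepts this for height and stops there. In the demographic table, one band such as BMI below 18.5 pools 13-year-olds and 17-year-olds, for whom the same BMI need not mean the same thing.

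What is at stake is how well a named safety variable can be read, and how well the population is described. The primary safety variables (TEAEs, and TEAEs leading to permanent withdrawal of study medication) are not affected.

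**Working it through.** The plan gives no figure to reproduce here: there is no sample size calculation, and the analysis is descriptive. The only formula needed is the SAP's own (6.1): "The BMI will be calculated as weight (kg) / (height (m"))², that is, kg/m².

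**Inputs from the documents:** age 13 to 17 years; entry weight at least 40 kg; lowest BMI limit 18.5; body size measured at Visits 5, 7 and 9 (protocol Table 5-1).

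**Assumptions, because the documents give no values:** starting heights of 150 to 170 cm, height gains of 0 to 8 cm, and a constant BMI of 20.

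**1. Who can fall in the lowest band.** BMI is below 18.5 when height exceeds √(weight/18.5).
- 40 kg: √(40/18.5) = 1.470 m
- 45 kg: √(45/18.5) = 1.560 m
- 50 kg: √(50/18.5) = 1.644 m

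Conversely, the weight at BMI 18.5 is 18.5 × height²: 41.6 kg at 150 cm, 47.4 kg at 160 cm, 53.5 kg at 170 cm and 59.9 kg at 180 cm. Eligible subjects can therefore fall in this band over a wide range of heights. The arithmetic does not show how many will, or whether they are normal for their age.

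**2. Weight change from height growth alone.** At constant BMI 20, the weight change is 20 × (h₁² − h₀²), with heights in metres.

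| Height gain | From 150 cm | From 160 cm | From 170 cm |
|---|---|---|---|
| 0 cm | 0 kg | 0 kg | 0 kg |
| 2 cm | 1.2 kg | 1.3 kg | 1.4 kg |
| 4 cm | 2.4 kg | 2.6 kg | 2.8 kg |
| 6 cm | 3.7 kg | 3.9 kg | 4.2 kg |
| 8 cm | 4.9 kg | 5.2 kg | 5.6 kg |

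**3. The same point in reverse.** A subject of 160 cm with BMI 20 weighs 20 × 1.60² = 51.2 kg. If that subject grows 4 cm and the weight does not change, BMI becomes 51.2/1.64² = 19.0. The listed weight change is zero, yet weight is 2.6 kg below what constant BMI would give, and the subject stays in the 18.5 to <25 band. Neither the raw change nor the band shows this.

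**4. What the reduced plan keeps.** SAP 10.3, 10.4.1 and 10.4.2 retain by-visit summaries of change from Baseline for hematology, chemistry, endocrine values (including IGF-1), blood pressure, pulse and seven ECG parameters. Body size has none. The SAP amendment log shows that the height percentile was added in the same amendment that reduced the displays. Growth referencing was thus judged worth having in the reduced plan, for one measure of three.

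**5. Age.** The only age the SAP derives is a whole number of years at consent (6.1). A percentile or z-score followed over months needs age at each measurement.

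**The case against.** The strongest reply has four parts.

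- **Growth is already referenced.** The CDC height percentile in SAP 10.4.1 tracks linear growth subject by subject. This stands. A reader might infer that no growth effect could be told from normal growth, but that goes too far: the gap is in weight and BMI, and in having no summary of the height percentile or its change. Nor are weight and BMI shown only as raw values, since the demographic table summarises them and the listings include change from Baseline. Those changes, however, carry no growth reference.
- **The bands do little harm.** A reader might infer that normal adolescents will be reported as underweight. The documents do not support that. The bands are unlabelled and define no criterion, subgroup or analysis set, and continuous BMI and age appear in the same table. The share of ordinary 13-year-olds below 18.5 would need a BMI-for-age distribution that the documents do not give, so none is estimated here.
- **Early termination explains the listing.** The SAP openly says that the analysis was cut, and mMIDI, menstrual function and neurological findings were also reduced to listings. This largely stands as a reason for having no summary table. It does not explain why a listing that already has a CDC percentile for height has none for weight or BMI. SAP 3.9 covers the departure from protocol 13.4.2 only in general terms.
- **There is no control arm.** A reader might infer that z-scores would let the study establish whether rotigotine affects growth. They would not: they adjust for expected growth but cannot attribute a departure to the drug. This stands and limits the claim to description.

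**Conclusion.** The point holds in limited form. The BMI bands in SAP 6.1 ignore age and sex in a 13- to 17-year-old population. SAP 10.4.1 applies its growth reference to height only, so changes in weight and BMI, both named safety variables, are not set against expected growth. Height is referenced, but only as a listed percentile without a summary.

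Under the stated assumptions, 2 to 8 cm of growth alone moves weight by 1.2 to 5.6 kg at constant BMI. That range illustrates scale; it is not an estimate for this trial, and shorter follow-up after early termination would make the movement smaller. The number of subjects who fall below 18.5 is unknown. The defect affects description and secondary safety reporting. It is worth correcting because the remedy is cheap.

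**What to change.** 1. **SAP 6.1:** replace or supplement the fixed bands with CDC BMI-for-age percentile categories (for example below the 5th, 5th to <85th, 85th to <95th, and 95th or above), and leave them without clinical labels.
2. **SAP 10.4.1:** derive CDC z-scores or percentiles for weight and BMI as well as height, using sex and age at each measurement. List them with change from the SP1006 Baseline.
3. **Summary:** add a short by-visit table of those changes if numbers allow after early termination. Otherwise, state in SAP 3.9 that listing only is a specific departure from protocol 13.4.2 for weight, height and BMI.
4. **Interpretation:** say that these displays are descriptive and cannot establish a drug effect on growth.

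The cost is SAP wording, a few derivations and one small table. Weight, height, sex and date of birth are already planned data items, so nothing new is collected. This assumes that the growth charts already cited also cover weight-for-age and BMI-for-age, and that birth dates are complete enough to give age at each visit.

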6.2 Other Baseline characteristics

Time since diagnosis of RLS will be derived in years applying all rules for missing date imputation as described in [Section 4.2.3](#) as integer ((date of informed consent - date of diagnosis) / 365.25).

Baseline characteristics will be listed only.

6.3 Family medical history

Family medical history will be listed for cases where a potential drug-induced liver injury (PDILI) is reported.

6.4 Prior and concomitant medications

Medications will be considered as prior if the start date of the medication is before the date of first patch administration (in RL0007). Medications will be considered as concomitant if it was taken at least once in the Treatment Period starting with the first patch administration and ending the day of last patch removal. Medications starting prior to first patch application and continuing into the Treatment Period will be considered both prior and concomitant medication.

For cases of partial or missing dates the rules described in [Section 4.2.2](#) will be applied.

Prior and concomitant medications will be summarized for the SS. The number and percentage of subjects who used prior or concomitant medications, respectively, will be presented according to the Anatomical Therapeutic Chemical main group, the therapeutic subgroup, and the preferred drug name.

7 MEASUREMENTS OF TREATMENT COMPLIANCE

Compliance will not be calculated for the early study termination scenario. Refer to [Section 10.1](#) for information about study medication exposure.

8 EFFICACY ANALYSES

All efficacy analyses will be performed for the SS and summarized by final dose group and all subjects combined.

8.1 Statistical analysis of key efficacy variables

The key efficacy variables are the changes from Baseline at EoM (Visit 9) in IRLS sum score, CGI Item 1 and RLS-6, but will be presented and analyzed together with all other visits. No imputation will be applied.

8.1.1 Derivations of key efficacy variables

The IRLS consists of 10 questions, each using a 5-point scale ranging from 0=not present to 4=severe. The IRLS sum score will be calculated by summing up the single scores of all applicable questions, i.e., the sum score will range between 0 and 40. If any answer is missing, the IRLS sum score will also be missing.

The CGI item 1 (Severity of Illness) scale ranges from 0 to 7 as follows: : 0=not assessed, 1=normal, not ill at all, 2=borderline ill, 3=mildly ill, 4=moderately ill, 5=markedly ill, 6=severely ill, 7=among the most extremely ill.

The RLS-6 Rating Scales (Kohnen, 2003) is designed to assess the severity of RLS and consists of 6 subscales. The subscales assess severity of symptoms at the following times of the day/evening: falling asleep, during the night, during the day at rest, and during the day when engaged in daytime activities. In addition, the subscales assess satisfaction with sleep and severity of daytime tiredness/sleepiness. Scores for each of the 6 subscales range from 0 (completely satisfied) to 10 (completely dissatisfied). No sum score will be calculated.

8.1.2 Analysis of the key efficacy variables

Summary statistics for observed values as well as changes from Baseline by visit will be provided for IRLS sum score, each subscale of the RLS-6 rating scales and CGI item 1.

9 PHARMACOKINETICS

9.1 Plasma concentration

Plasma samples will be collected at Visit 5 and Visit 9. The results of plasma concentrations of unconjugated rotigotine will be presented in a listing.

9.2 Population Pharmacokinetics

The plasma concentrations of unconjugated rotigotine may also be used for population PK-PD analyses. Details and methods of these analyses will be described in the Data Analysis Plan and the results will be reported in a separate modeling report.

10 SAFETY ANALYSES

All safety analyses will be conducted for the SS and results will be presented by final dose group and for all subjects combined.

